4 STUDY DESIGN

Work Package 1: Mapping Health Service Characteristics.

Information on the characteristics of English acute NHS hospital trusts, including staffing and configuration of gastroenterology and hepatology service provision will be collated from multiple

NHS Foundation Trust

existing sources. These sources will be supplemented by hospital trust-level data collected through direct contact with individual hospital trusts. This organisational survey will be the source of information on health service characteristics at provider, clinical network and regional levels.

Existing sources of hospital trust-level information:

1. National Confidential Enquiry into Patient Outcome and Death (NCEPOD) Alcohol-related Disease Survey.

This survey is currently ongoing, and its submission is mandatory for all Acute hospital trusts in the United Kingdom as part of the NHS Quality Accounts. Data from the survey is expected to be complete in the spring of 2022. It follows up the 2013 NCEPOD report "Measuring the Units" on the care of patients with alcohol-related CLD liver disease with focus on key areas of current service provision and practice relevant to the acute care of patients with CLD from all causes.

Details of hospital trust-level service configuration includes whether a specialist or non-specialist team is delivering care to patients admitted with decompensated cirrhosis of all aetiologies, the presence and availability of a specialist Alcohol Care Team, participation in liver clinical networks and the relationship with a specific liver transplant unit. Details of hospital trust practices includes utilisation of the BASL Care Bundle of early evidence-based interventions and the 24/7 availability of on-site endoscopic treatment for variceal bleeding. A subjective assessment of difficulties encountered in the admission to ICU of patients with decompensated alcohol-related liver disease is also provided.

2. Royal College of Physicians Consultant Census (RPCCC).

This national annual census has been undertaken by the Royal College of Physicians (RCP) since 2004 with data now available for the 2018/19 census. It is anticipated that data from the 2020/21 census will be available in early 2022. Census returns are supplemented via an information exchange with the General Medical Council with near complete coverage of the UK consultant workforce. It provides hospital trust-level detail on the number and speciality of consultant staff in post, their clinical workload, and how these have changed over time.

3. Improving Quality in Liver Services (IQILS) accreditation standards evidence.

Improving Quality in Liver Services (IQILS) is a programme run by the RCP and supported by professional bodies and patient groups. Established in 2017, participating hospital trusts seek accreditation by demonstrating achievement of specific organisational and clinical standards for the care of patients with liver disease.

As such, each hospital trust provides evidence of the detail of the current configuration of liver disease services and of the clinical performance against key performance standards, developed by BASL and NICE. To date 56 hospital trusts have achieved accreditation and by 2022 it is anticipated that this number will have risen to approximately 100.

4. Intensive Care National Audit and Research Centre unit-level information

The Intensive Care National Audit and Research Centre (ICNARC) maintains a high-quality database containing unit-level information including type of unit and number of beds, derived bed occupancy and measures of case mix.

5. British Association for the Study of Liver Disease (BASL) national audit.

In 2018 and 2019, BASL undertook a detailed survey of the configuration and provision of hepatology services in acute NHS hospital trusts. Responses were received from 126 hospital trusts and detail

King's College Hospital MHS

NHS Foundation Trust

medical and nursing staffing arrangements, in-hours and out-of-hours specialist service and procedure provision (including endoscopy and transjugular intrahepatic portosystemic shunt), and participation in clinical network arrangements for urgent referrals, emergency transfers and liver transplantation. Clinical networks are well characterised, and hospital trusts are classified into network participants and non-participants, referral sites, regional centres, and transplantation centres.

6. NHS England Datasets

Other relevant hospital trust-level characteristics to be included from NHS England datasets will be the relevant hospital size in beds, bed occupancy and transplant centre status.

Time period considerations

Up-to-date organisational characteristics of bed numbers, occupancy and transplant status will be available throughout the study period but characteristics from some data sources will need to be updated through direct contact with NHS hospital trusts.

Work Package 2: Understanding Determinants of Variation in Practice and Outcomes after Emergency Hospital Admission.

The study will use linked existing electronic patient-level healthcare data to map the full "patient journey" of patients with CLD. The patient journey will start from the first emergency hospital admission and we will examine determinants of Intensive Care Unit (ICU) admission, length of stay, inter-hospital transfer for specialist care or liver transplantation and in-hospital and longer term mortality.

We will use three existing national datasets linked at patient-level:

- Hospital Episodes Statistics (HES) data (inpatient, outpatient data, A&E attendances and ONS mortality data)
- Intensive Care National Audit and Research Centre Case Mix Programme (ICNARC-CMP) database
- UK Transplant Registry maintained by NHS Blood and Transplant

The research team analysing the data will not have access to patient identifiers. Please see the Data Flow Diagram attached as appendix 2.

We will include all adult patients with CLD disease who were admitted with a first emergency hospital admission in the study period from 1 April 2009 to 31 March 2022 according to HES-APC data, with an expected cohort size of about 100,000 CLD patients. Patients will be considered to have CLD according to ICD-10 diagnostic codes.

Explicit coding schemes will be developed. We will create coding schemes that describe the clinical characteristics of the patients, including the nature and severity of the CLD, their comorbidities, and their adversity-related health issues. Coding schemes will also be developed to capture critical care admissions, predominantly based on data items available through linkage with ICNARC data but enhanced by also including information available in HES records of hospital admission and adult critical care episodes. In addition, we will derive measures that capture specific patterns of secondary care use in the year immediately after the first emergency admission, in terms of the number of planned outpatient visits, A&E attendances, planned and emergency readmissions, and the total time spent in hospital.

We now outline how we will address each of the specific objectives listed in section 3.1.

1. Time trends in acute secondary care for patients with chronic liver disease and its outcomes:

We will use the linked datasets to describe for each year in the study period the number of CLD patients who had an emergency admission, the proportion of these patients who had an admission to critical care and its duration, total length of hospital stay, readmission rate and total time spent in hospital within the first year, the rate of liver transplantation, and in-hospital and 1-year mortality.

2. Regional variation in acute secondary care for patients with chronic liver disease and its outcomes: We will estimate in the last 5 years of data the rate of emergency admissions for CLD per 100 000 people per year in 44 regions of England. We will estimate regional emergency admission rates without and with adjustment for patient and regional characteristics. In addition, we will analyse regional differences in outcomes.

3. Impact of regional clinical networks on referral patterns: The development of regional networks, shaped as hub-and-spoke models, will be explored by observing referral patterns after a first emergency admission of patients with CLD. We will identify the hub (a hospital that typically receives referrals) and the spokes (hospitals that typically refer patients) in each clinical network. The configuration and characteristics of these networks will be compared.

4. Impact of regional, hospital and patient characteristics on critical care use of chronic liver disease patients who had a first emergency admission: Multilevel logistic regression models will be used to explore which of the regional characteristics, hospital characteristics, and patient characteristics are associated with critical care use.

5. Critical care use and clinical outcomes after a first emergency admission in patients with CLD:

We will characterise hospitals according to the proportion of patients that are admitted to critical care and whether they were admitted to critical care early or late in order to explore to what extent hospitals with more frequent and earlier critical care admissions of CLD patients after an emergency admission have better short-term outcomes. The results will be analysed using multilevel logistic regression including the level and timing of critical care use as hospital-level characteristics with adjustment for key patient characteristics.

6. Use of liver transplantation after a first emergency admission in patients with CLD: Using the linked UK Transplant Registry data, we will explore the regional variation in the use of liver transplantation in the first year after a first emergency admission. We will use multilevel logistic regression models to explore to what extent the regional variation is associated with specific patient and health service characteristics.

7. Impact of coordinated specialist outpatient review after discharge on readmissions, referral for transplantation, and mortality: To answer this question, we will compare the outcomes of patients who are discharged alive from hospital after their first emergency admission from hospitals that offer coordinated specialist outpatient review with patients from hospitals where this type of outpatient review is not available. We will use multilevel Cox regression to estimate differences in time to readmission, referral for transplantation, and death.

5 STUDY SCHEDULE

Please see section 4 above and monthly time line attached as appendix 1

6 CONSENT

Not applicable: study working with existing routine data only.

Application is being made for Section 251 support from CAG.

7 ELIGIBILITY CRITERIA

7.1 Inclusion Criteria

The study will include all patients older than 18 years with chronic liver disease (CLD) who were admitted with a first emergency hospital admission between 1 April 2009 and 31 March 2022.

7.2 Exclusion Criteria

A previous emergency hospital admission with chronic liver disease in the two preceding years.

People who have chosen to adopt the National Data Opt-Out.

8 **RECRUITMENT**

Not applicable: study working with existing routine data only.

A data flow diagram is appended as Appendix 2.

Hospital Episode Statistics (HES) data will be requested from NHS Digital for patients with a Chronic Liver Disease (CLD) diagnosis anywhere in their episodes in the study period (1 April 2009 to 31 March 2021). CLD diagnosis will be defined as ICD-10 codes in the range between B15-B19 or between K70-K77.

Analysts at NHS Digital will identify the patient cohort. They will send the identifiers of these patients (without any clinical data) to the Intensive Care National Audit and Research Centre (ICNARC) for linkage to ICNARC data.

Patients undergoing a liver transplant in England between one year before the study period to one year after the study period will be identified in The UK Transplant Registry, by NHS Blood and Transplant. The identifiers of these patients will be sent (without clinical data) to NHS Digital for linkage to HES.

De-identified cohorts of patients will be sent from NHS Digital, ICNARC and NHS Blood and Transplant to LSHTM for analysis, containing no patient identifiers. Pseudonymised study IDs will be used by the research team at LSHTM to link the three datasets.

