9 STATISTICAL METHODS

Please see section 4 above. Further, an overview of the statistical plan is presented below.

King's College Hospital NHS

NHS Foundation Trust

We will include all patients older than 18 years with chronic liver disease (CLD) who were admitted with a first emergency admission (EA) in the study period from 1 April 2009 to 31 March 2022. Patients will be considered to have CLD if they have a Hospital Episode Statistics (HES) inpatient record with an ICD-10 codes in the range between B15- B19 or between K70-K77. An EA will be identified based on an administrative HES code related to the method of admission. We will consider an EA to be a first-time occurrence if there is no record of a similar admission, with a minimum of in two preceding years of data available (the "look-back" period).

We will create coding schemes that describe the clinical characteristics of the patients, including the nature and severity of the CLD, their comorbidities, and their adversity-related health issues. Coding schemes will also be developed to capture critical care admissions, predominantly based on data items available through linkage with Intensive Care National Audit and Research Centre (ICNARC) data but enhanced by also including information available in HES records of hospital admission and adult critical care episodes. In addition, we will derive measures that capture specific patterns of secondary care use in the year immediately after the first EA, in terms of the number of planned outpatient visits, and A&E attendances, the number of planned and emergency readmissions, and the total time spent in hospital.

Specific research questions:

1. Time trends in acute secondary care for patients with chronic liver disease and its outcomes:

We will use the linked datasets to describe for each year in the study period from 1 April 2009 to 31 March 2022, the number of CLD patients who had an EA, the proportion of these patients who had an admission to critical care and its duration, total length of hospital stay, readmission rate and total time spent in hospital within the first year, the rate of liver transplantation, and in-hospital and 1-year mortality. Changes in these results over time (including changes in the period 2020-2022 as a result of the Covid-19 pandemic) will be determined with Poisson, logistic or linear regression models, depending on the nature of the dependent variable.

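### Section 8 selects patients on CLD diagnoses up to 31 March 2021, but the cohort and pandemic analyses run to 31 March 2022, so 2021/22 first admissions would be incompletely and selectively captured

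*Protocol*

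**What the plan says.** Section 8 (Recruitment), printed directly after the exclusion criteria of 7.2, describes the data request. Patients are picked out by a CLD "diagnosis anywhere in their episodes in the study period (1 April 2009 to 31 March 2021"). NHS Digital identifies the cohort on that basis and sends the identifiers to ICNARC for linkage. The UK Transplant Registry is searched from one year before to one year after the study period, with no dates given.

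Everywhere else the period ends a year later:

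- Section 4: "first emergency hospital admission in the study period from 1 April 2009 to 31 March 2022 according to HES-APC data".
- Section 7.1: "first emergency hospital admission between 1 April 2009 and 31 March 2022".
- Section 9: "first emergency admission (EA) in the study period from 1 April 2009 to 31 March 2022".
- The Study Overview table gives the same end date, 31 March 2022.

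Section 9, question 1, reports results "for each year in the study period from 1 April 2009 to 31 March 2022", "including changes in the period 2020-2022 as a result of the Covid-19 pandemic". The outcomes include "readmission rate and total time spent in hospital within the first year, the rate of liver transplantation, and in-hospital and 1-year mortality". Section 9 also derives "measures that capture specific patterns of secondary care use in the year immediately after the first EA". No end date is given for the HES or ONS records themselves.

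**The concern.** One defined term has two end dates, and the outlying date sits in the operative instruction. A data request made to Section 8 could not deliver the analyses in Section 9.

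The loss would not be random. Section 2 notes that people with CLD often first come to attention through an emergency admission. Those are the patients with no earlier code, and they are the ones a 2021 cut-off would miss. Any 2021/22 patients still selected would be people already coded with CLD, a different case mix from earlier years. The admission count for 2021/22 would fall, and its outcomes would describe a selected group. Both changes fall inside the period meant to show the effect of Covid-19.

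**Working it through.** **Inputs.** About 9,000 first emergency admissions a year (Section 2). Cohort about 100,000 (Study Overview and Section 4). Start 1 April 2009. End 31 March 2021 (Section 8) or 31 March 2022 (Study Overview, Sections 4, 7.1 and 9). Outcomes over one year (Section 9).

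**1. Does the stated cohort size show which date was meant?** Years × 9,000:

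- to 31 March 2022: 13 × 9,000 = 117,000 (17% above 100,000)
- to 31 March 2021: 12 × 9,000 = 108,000 (8% above)
- 11 years, if the first two served only as look-back: 11 × 9,000 = 99,000 (1% below)

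Neither stated window gives 100,000 closely. The figure is rounded, and Section 1 says more than 100,000. It is not an error and does not settle the end date.

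**2. Size of the gap.** The dates differ by 12 months, so 117,000 − 108,000 = 9,000 admissions, and 9,000/117,000 = 1/13 = 7.7%. Of the 24 months from April 2020 to March 2022, 12/24 = 50% are affected (12/27 = 44% if counted from January 2020).

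**3. How many would be missed.** A patient first admitted in 2021/22 who already had a CLD-coded episode before April 2021 still meets the Section 8 rule. Let f be the share of such patients. The number not selected is 9,000 × (1 − f). The protocol gives no f, so these values are assumptions:

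| f (assumed) | Not selected |
|---|---|
| 0 | 9,000 |
| 0.1 | 8,100 |
| 0.3 | 6,300 |
| 0.5 | 4,500 |

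Over this range the 2021/22 count would be short by 50% to 100%, or 3.8% to 7.7% of the 117,000.

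**4. Follow-up, by calendar arithmetic.** The protocol states no HES or ONS end date, so three are tried:

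| HES/ONS records end (assumed) | Last admission with a full year | Complete months, April 2020 to March 2022 |
|---|---|---|
| 31 March 2021 | 31 March 2020 | 0 of 24 |
| 31 March 2022 | 31 March 2021 | 12 of 24 |
| 31 March 2023 | 31 March 2022 | 24 of 24 |

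**5. Registry margin.** One year after the study period is 31 March 2022 under the Section 8 date and 31 March 2023 under the date used elsewhere. Only the later date gives a full transplant year to admissions at the end of the cohort.

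**The case against.** The strongest reply is that this is one wrong year against four consistent statements, and that the analysts would follow the majority. A slip is plausible, but the protocol cannot confirm it, and the outlying date is in the passage that governs selection.

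The other objections are aimed at stronger readings that a reader might infer, and they stand:

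- **That the HES extract ends on 31 March 2021.** The dates say when a diagnosis selects a patient, not when that patient's records stop. The two-year look-back for April 2009 admissions needs data from about April 2007, before the window opens, so the window is evidently not the limit of the records supplied.
- **That the whole 2021/22 year is lost.** Previously coded patients would still be selected, so 9,000 is an upper bound.
- **That 1-year outcomes are truncated by a known amount.** If records stopped at the end of the last admission year, an assumed true readmission risk of 50% would be recorded as about 28% to 34%, depending on the assumed hazard shape. That rests on a cut-off the protocol does not state and on an assumed risk. It also ignores death as a competing event, although Section 2 says over a quarter die within 60 days.
- **That transplants would fall artefactually in 2020/21.** The registry has a margin of one year, so even on the 2021 date those admissions have a full transplant year.
- **That the planned models cannot handle partial follow-up.** Poisson regression accepts person-time offsets, and the Cox models in question 7 handle censoring.

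**Conclusion.** The contradiction is real and should be corrected before the request is relied on. Followed literally, Section 8 under-ascertains first admissions from April 2021 to March 2022 and does so selectively. Up to about 9,000 patients are affected, at most 7.7% of the cohort. The figure is 4,500 to 9,000 if between none and half were already coded, a range that is assumed. The affected year is half of the April 2020 to March 2022 period. The figures rest on the protocol's own 9,000 a year, taken as constant.

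Incomplete 1-year follow-up is a separate and conditional point. It arises only if HES and ONS records stop at the end of the study period. The protocol leaves that open, giving a margin for the transplant registry and no end date for HES or ONS.

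**What to change.** In Section 8, change the end of the study period to 31 March 2022, to match the Study Overview and Sections 4, 7.1 and 9. The registry margin of one year then runs to 31 March 2023.

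In the same correction, separate the selection window from the record window. Request HES inpatient, outpatient, A&E and critical care records and ONS deaths to 31 March 2023, so that the 1-year outcomes are complete for every admission. If later records cannot be supplied, restrict 1-year outcomes to admissions at least 12 months before the end of data.

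If the request has already been submitted, check which end date it carried.

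The cost is a text correction and a later end date in the request, or one restriction rule in the analysis. No new data source is needed. Finding the mismatch after extraction could mean a second request and repeat linkage.

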9 STATISTICAL METHODS

Please see section 4 above. Further, an overview of the statistical plan is presented below.

King's College Hospital NHS

NHS Foundation Trust

We will include all patients older than 18 years with chronic liver disease (CLD) who were admitted with a first emergency admission (EA) in the study period from 1 April 2009 to 31 March 2022. Patients will be considered to have CLD if they have a Hospital Episode Statistics (HES) inpatient record with an ICD-10 codes in the range between B15- B19 or between K70-K77. An EA will be identified based on an administrative HES code related to the method of admission. We will consider an EA to be a first-time occurrence if there is no record of a similar admission, with a minimum of in two preceding years of data available (the "look-back" period).

We will create coding schemes that describe the clinical characteristics of the patients, including the nature and severity of the CLD, their comorbidities, and their adversity-related health issues. Coding schemes will also be developed to capture critical care admissions, predominantly based on data items available through linkage with Intensive Care National Audit and Research Centre (ICNARC) data but enhanced by also including information available in HES records of hospital admission and adult critical care episodes. In addition, we will derive measures that capture specific patterns of secondary care use in the year immediately after the first EA, in terms of the number of planned outpatient visits, and A&E attendances, the number of planned and emergency readmissions, and the total time spent in hospital.

Specific research questions:

1. Time trends in acute secondary care for patients with chronic liver disease and its outcomes:

We will use the linked datasets to describe for each year in the study period from 1 April 2009 to 31 March 2022, the number of CLD patients who had an EA, the proportion of these patients who had an admission to critical care and its duration, total length of hospital stay, readmission rate and total time spent in hospital within the first year, the rate of liver transplantation, and in-hospital and 1-year mortality. Changes in these results over time (including changes in the period 2020-2022 as a result of the Covid-19 pandemic) will be determined with Poisson, logistic or linear regression models, depending on the nature of the dependent variable.

2. Regional variation in acute secondary care for patients with chronic liver disease and its outcomes:

First, we will estimate the rate of EAs for CLD per 100 000 people per year in 44 regions. The numerator will be the number of CLD patients with a first EA and the denominator populations will be derived by aggregating the updated 2011 Census results for patients of 18 years and older in each region. We will use multilevel Poisson regression models to produce empirical Bayes estimates for regional EA rates without and with adjustment for patient and regional characteristics. We will analyse regional differences in critical care use during the EA, total length of hospital stay, readmission rate and total time spent in hospital within the first year, the rate of liver transplantation, and in-hospital and 1-year mortality. Multilevel regression models will be used to quantify the regional variation and to produce empirical Bayes estimates for each region. We will assess the impact of the Covid-19 pandemic on regional variation in EA rates and outcomes.

3. Impact of regional clinical networks on referral patterns: The development of regional networks, shaped as hub-and-spoke models, will be explored by observing referral patterns after a first EA of patients with CLD. We will create "super-spells" for each patient and identify within this super-spell the hospital of the EA and the hospital trust where most of the care was provided. These results will be used to identify the hub (a hospital that typically receives referrals) and the spokes (hospitals that typically refer patients) in each clinical network. The configuration and characteristics of these networks (e.g., in terms of regional coverage, number and characteristics of referred patients, type of

care provided predominantly in the hub and spokes, changes to referrals pre- and post- Covid-19)) will be compared.

4. Impact of regional, hospital and patient characteristics on critical care use of chronic liver disease patients who had a first emergency admission: We will explore the association between which of the regional characteristics (e.g., network arrangements, prevalence of CLD, use of transplantation), hospital characteristics (e.g., transplant centre status, specialist staffing, ICU capacity, ICU case-mix), and patient characteristics (e.g., type of CLD and comorbidity, age, sex, socioeconomic deprivation) are associated with the proportion of cases admitted to critical care, their clinical condition at critical care admission, the duration of critical care, and the proportion of cases for whom critical care was withdrawn. We will also explore changes in critical care use as a result of the Covid-19 pandemic. Multilevel logistic regression models will be used to estimate adjusted odd ratios that capture the impact of the regional, hospital and patient characteristics and the Covid-19 pandemic on critical care use.

5. Critical care use and clinical outcomes after a first EA in patients with CLD: We will characterise hospitals according to the proportion of patients that are admitted to critical care and whether they were admitted to critical care early or late in order to explore to what extent hospitals with more frequent and earlier critical care admissions of CLD patients after an EA have better short-term outcomes (in-hospital mortality and readmissions, total time spent in hospital and mortality during the year following the EA). The results will be analysed using multilevel logistic regression including the level and timing of critical care use as hospital-level characteristics with adjustment for key patient characteristics, including age, sex, socioeconomic deprivation, and comorbidity.

6. Use of liver transplantation after a first EA in patients with CLD: Using the linked UK Transplant Registry data, we will explore the regional variation in the use of liver transplantation in the first year after a first EA. We will use multilevel logistic regression models to explore to what extent the regional variation is associated with specific patient and health service characteristics , and whether patterns of transplantation changed in response to the Covid-19 pandemic. We will use Cox regression with sequential stratification to estimate the impact of liver transplantation on survival. Sequential stratification is a relatively new method which has wide applicability to observational studies where the time to an event (e.g., death) is of interest and the treatment being compared (i.e., liver transplant) is time dependent.

7. Impact of coordinated specialist outpatient review after discharge on readmissions, referral for transplantation, and mortality: We will compare the outcomes of patients who are discharged alive from hospital after their first EA from hospitals that offer coordinated specialist outpatient review with patients from hospitals where this type of outpatient review is not available. We will use multilevel Cox regression to estimate differences in time to readmission, referral for transplantation, and death.

